The Relationship between MRI Diagnosis and Psychosocial Factors in Physiotherapy Treated Chronic Non-Specific Low Back Patients. A Mixed Method Study

Short title:	The Psychosocial	Impact of MRI	Diagnosis in	n Chronic N	on-Specific
Low Back Pai	n	-	_		-

Acronym: Psychosocial-factors

FMHS REC reference:

Study Sponsor: University of Nottingham

Funding Source: Prince Sattam Bin Abdulaziz University

STUDY PERSONNEL AND CONTACT DETAILS

Sponsor: University of Nottingham

Chief investigator: [name]

PhD Student

University of Nottingham

Division of Rehabilitation and Ageing

[name]

Queen's Medical Centre (QMC)

[name]

[contact] [contact]

Email: [contact]

Co-investigators: [name]

Professor in Health Psychology

University of Nottingham

Division of Rehabilitation and Ageing

[name]

Queen's Medical Centre (QMC)

[name]

[contact]

[contact]

Email: [contact]

[name]

Associate Professor in Rehabilitation Research (Long Term Conditions)

University of Nottingham

Division of Rehabilitation and Ageing

[name]

Queen's Medical Centre (QMC)

[name]

[contact]

[contact]

Email: [contact]

Study Statistician: [name]

PhD Student

University of Nottingham

Division of Rehabilitation and Ageing

[name]

Queen's Medical Centre (QMC)

[name]

[contact] [contact]

Email: [contact]

Study Coordinating Centre:

SYNOPSIS

Title	The Relationship between MRI Diagnosis and Psychosocial Factors in Physiotherapy Treated Chronic Non-Specific Low Back Patients. A Mixed Method Study
Acronym	Psychosocial Factors
Short title	The Psychosocial Impact of MRI Diagnosis in Chronic Non-Specific Low Back Pain
Chief Investigator	[name]
Objectives	 Identifying psychosocial factors associated with MRI diagnosis in people with NS-CLBP. To study the relationship between identified psychosocial factors and MRI diagnosis in people with CLBP. To explore knowledge among healthcare professionals in clinical guideline of imaging for NS-CLBP in Saudi Arabia. The primary objective is to assess the feasibility of randomizing patients to two groups in terms of patients' acceptance, physicians' acceptance and healthcare reliance. To estimate the recruitment rate and describe reasons for non-recruitment. To assess the integrity of the study protocol To appropriately estimate the sample size needed for the definitive RCT.

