cortical representation of neuron firing in chronic pain patients how found that these patients display

more neurons firing in the memory area when they asked to imagine doing daily activities whereas

control group showed more firing in the motor areas. Chronic back pain patients tend to display a

heightened fear of movement (kinesiophobia) and increased depression (George and Beneciuk, 2015).

The Saudi Arabian context

The healthcare system in Saudi Arabia is government-funded and publically available to all; 79% of

all patients receive treatment in the public system while the remainder are treated privately (Almalki et

al., 2011). Insurance companies cover the majority of private patients. The public healthcare system is

structured into three levels: primary, secondary and tertiary. Advanced radiological investigations are

not available at the primary level.

CLBP patients in Saudi Arabia have the option of directly seeking medical treatment in the private

system, thus bypassing the primary triage level. A study performed in a 440-bed university hospital in

the eastern region of Saudi Arabia showed that the average number of MRI assessments performed

annually was 2725, with the highest proportion attributed to adult orthopaedic and spine referrals;

these figures have increased yearly since 2007 (Jabali et al, 2015). This hospital is considered small in

comparison to the referenced medical cities in the region, which serve 1200 beds. Nonetheless,

university hospital practitioners could be expected to have a good awareness of the literature and

guidelines.

McCullough et al. (2012) demonstrated that lower back pain patients who receive MRI reports without

also receiving information of the likelihood of false positive results were more likely to be prescribed

pain medication than those who had received information on asymptomatic prevalence. The increased

prescription of medication was associated with increased symptoms. With the knowledge that

psychological factors have a significant influence in NS-CLBP, and that MRI results can instigate a

Page 10 of 28

change in symptoms as well, it will be interesting to determine whether pain is preceded by

psychological changes.

STUDY OBJECTIVES AND PURPOSE

PURPOSE

This study aims to identify the psychosocial factors associated with MRI diagnosis in patients with

non-specific low back pain. It will explore the experience of this group of patients in Saudi Arabia and

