the healthcare providers who are in direct contact with their treatment.

PRIMARY OBJECTIVE

Qualitative study:

To explore psychosocial factors associated with receiving MRI diagnosis in people with NS-

CLBP in Saudi Arabia.

To explore current practice in the use of MRI imaging amount healthcare professionals

(physiotherapist and doctors) in NS-CLBP.

Quantitative Study:

The primary objective is to assess the feasibility of randomizing patients to

two groups in terms of patients' acceptance, physicians' acceptance and

healthcare reliance.

To estimate the recruitment rate and describe reasons for non-

recruitment.

To assess the integrity of the study protocol

To appropriately estimate the sample size needed for the definitive RCT.

Page 11 of 28

Process evaluation:

An embedded process evaluation will explore:

The acceptability of randomization from the perspective of patients and

healthcare professionals involved in trial delivery

• What aspects of the larger social, political, and economic environment

might have influenced trial delivery and intervention implementation?

STUDY DESIGN

STUDY CONFIGURATION

A sequential exploratory mixed methods design in which both qualitative and quantitative research

methods will be employed in this project. There will be two sequential parts: 1) focus group (FG) or

interviews with people with LBP and service providers (Part I), a feasibility RCT (Part II) with an

embedded process evaluation.

Part I: There will be three FG interviews of people with NS-CLBP, physiotherapists and doctors. The

focus groups shall be held in the conference room of King Fahad Medical City, after obtaining

approval from hospital management. The data from these focus groups will help in identifying the

main psychosocial factors associated with receiving MRI diagnosis in people with NS-CLBP.

Moreover, the data from the FG or interview of health professionals (physiotherapists and physicians)

will help in understanding the current practice of using MRI as a diagnostic tool in people with NS-

CLBP. Since we are considering the experience of multiple fields, conducting an FG will be

appropriate for collecting data from a large sample in a relatively short time; in addition, the FG

encourages interaction between the participants. If the formation of focus group is not applicable, then

we shall conduct one to one interviews.

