the study. Each group will contain six to eight clinicians, male and female. If FG is not possible,

especially with physician, then one to one interview will be performed.

Part II:

In Part II of the study, [name] will approach the administrators at King Fahad Medical

City for approval to conduct the second part of the study. The lead physician will invite all patients

who met the inclusion criteria to take part in the study using the patients register program. An ethical

consent form and an information sheet will be handed to the patients. [name] will be

responsible to answer any question participants may have before signing the consent. A signature is

required from each patient to document his/her acceptance to enrol in the study. To ensure equal

distribution between groups, block randomization schedule will be used to assign patient into groups;

MRI group and control group. The MRI group will have MRI scan and discuss the result with their

doctors before having the physiotherapy treatment. The control group will have physiotherapy

treatment without MRI scan.

Process Evaluation:

Patient particepent of Part II, will be invited by email to participate in process evaluation interviews.

Additional consent forms and information sheets related to this study will be emailed to participants.

Reply from the participant with the approval is required t to document his/her acceptance to enrol in

the study. [name] will be responsible to answer any questions concerning these

documents.

The research team in King Fahad Medical City, including doctors and physiotherapists, will be invited

by email to participate in interview study to evaluate their experiences of the feasibility RCT. Mr

[name] will be responsible for contacting the research team and explaining the study aims.

For the focus groups and interviews:

Inclusion criteria:

Patient participants:

Male and female aged 18 to 65 years, CLBP with no clear medical diagnosis who had an MRI scan

and a report for LBP in the last month (e.g., malignancy, fracture, infection, spinal stenosis,

sponylosthesis or inflammatory disease). Chronicity will be considered if the pain has persisted for

more than three months.

Clinician participants:

Page 16 of 28

Physicians in direct contact with people with NS-LBP and with the authority to refer patients for MRI

will be recruited as clinician participants. Inclusion criteria for physiotherapists include outpatient

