physiotherapists with a primary interest in LBP management.

Exclusion criteria:

Women who are pregnant or less than six months postpartum, or have received pain-relieving

procedures (injection or denervation) in the previous three months or have evidence of neurological

impairment will be excluded from the study.

For the feasibility RCT:

Inclusion criteria:

Male or female aged 18 to 65 years; CLBP with no clear medical diagnosis who had an MRI scan and

a report for LBP in the last month (e.g., malignancy, fracture, infection, spinal stenosis, sponylosthesis

or inflammatory disease) will be included. Chronicity will be considered if the pain has persisted for

more than three months. Patients must not have had physiotherapy treatment in the six months prior to

the study.

Exclusion criteria:

Women who are pregnant or less than six months postpartum, or have received pain-relieving

procedures (injection or denervation) in the previous three months or have evidence of neurological

impairment will be excluded from the study.

Participant withdrawal

Participation in this study is voluntary. All participants are free to withdraw from the study at any

time, without fear of penalty of impact on their healthcare and the researcher could remove

participants from the study if needed as well. If there is a withdrawal from the study, the information

collected prior to the withdrawal will not be removed and shall be used in the analysis. The treatment

given to the patients will not be affected by their withdrawal from the study. Patients who drop out of

the study will not be replaced.

Page 17 of 28

The Psychosocial Impact of MRI Diagnosis in Chronic Non-Specific Low Back Pain

Study ID/ Psychosocial -Factors

Informed consent

The consent form must be signed and dated prior to participating in the study. The CI will explain the

study by providing an information sheet and answering the questions of the patients and clinicians.

Both healthcare practitioners and patients will be contacted during and after the feasibility trial asking

if they would be willing to take part in an interview at the end of the trial, about their experiences of

taking part in the trial, the process of the trial and factors affecting its delivery.

STUDY REGIMEN

Compliance

Participation in the FG and the returned handbook of outcome measures are the indictors for

compliance.

Criteria for terminating the study

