Again, they will have the option to withdraw from the study if they feel it is appropriate to do so. If

participants are very distressed, they will be referred to their GPs.

PROCESS EVALUATION

We will conduct a process evaluation alongside the feasibility RCT to explore the acceptability of

randomisation and the study design with both healthcare practitioners involved in trial delivery and

Page 19 of 28

The Psychosocial Impact of MRI Diagnosis in Chronic Non-Specific Low Back Pain

Study ID/ Psychosocial -Factors

patient participants. Interviews will also explore the broader social, political, economic and environmental (context) aspects that may have influenced trial delivery and intervention implementation. The process evaluation will use quantitative data from the recruitment process collected by the research team and qualitative data from participants' interviews.

Quantitative data:

The participating centre will be described in term of number of doctors, supporting staff and caseload.

The number of participants will be recorded to describe the rate of participation, attrition and drop out.

Qualitative data:

Interviews will explore the acceptability of the study design to both patient participants and healthcare practitioners involved in the trial delivery. Furthermore, it will explore the contextual aspects of implementing the study.

Telephone semi-structured interview will be conducted by ([name]) with purposive sample of 4-6 patients and 2-4 healthcare practitioners and research staff in each centre participating in the feasibility study.

All interviews will be audio- recorded and transcribed verbatim and analysed thematically using NVivo software. Validity of the obtained data will be assured by triangulating the findings with participants.

ETHICAL AND REGULATORY ASPECTS

ETHICS COMMITTEE AND REGULATORY APPROVALS

The study will commence after the study protocol, consent form and participant information sheet are approved from the (REC). Modification of the protocol after REC approval will require another full review of all of the documents. If the amendment involves eliminating an adverse event to the participants, the REC will be notified immediately and an updated approval will be sought. Amendments that do not have a major effect on the protocol might be implemented first and REC subsequently notified.

The study shall follow the Declaration of Helsinki (1996) in the Ethical Principles of Conducting

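### Compliance for trial patients is defined as booklet return alone, so no quantitative measure shows, by arm, whether patients received the MRI or no-MRI pathway they were allocated

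*Protocol*

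**What the plan says.** - **Compliance rule.** Study Regimen, Compliance: "Participation in the FG and the returned handbook of outcome measures are the indictors for" compliance. It is one sentence covering both parts of the study.
- **What separates the arms.** Recruitment, Part II: "The MRI group will have MRI scan and discuss the result with their" doctors before physiotherapy starts, while controls have physiotherapy "treatment without MRI scan".
- **Objectives.** Under Quantitative Study: "The primary objective is to assess the feasibility of randomizing patients to" two groups, judged by patients' acceptance, physicians' acceptance and healthcare reliance. Further objectives are "To assess the integrity of the study protocol" and to estimate the sample size for the definitive RCT.
- **Planned process data.** Process Evaluation, Quantitative data, describes the centre's staffing and caseload and then says "The number of participants will be recorded to describe the rate of participation, attrition and drop out". Under Qualitative data, "Interviews will explore the acceptability of the study design to both patient participants and healthcare practitioners involved in the trial delivery". The interviews involve 4-6 patients and 2-4 practitioners.
- **Context.** The Saudi Arabian context: "CLBP patients in Saudi Arabia have the option of directly seeking medical treatment in the private" system, bypassing primary triage. The background section adds that clinicians continue to request imaging despite guideline consensus.

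**The concern.** The rule measures whether a form came back. It does not measure whether the MRI arm was scanned and had the result discussed before physiotherapy, whether controls stayed unscanned, or whether either arm attended physiotherapy. Those events are what the randomisation is meant to control.

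Two things are at stake. First, the feasibility RCT could report full compliance although allocation was not followed, which would mislead on protocol integrity and on whether randomising is workable. Second, the definitive RCT would be sized with no information on how far crossover and non-receipt dilute the contrast between arms. The protocol's own background makes control-arm scanning foreseeable. A private scan may not appear in the hospital record unless the patient is asked.

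**Working it through.** The protocol gives no compliance figure to reproduce. The check is therefore a comparison of texts, followed by illustrations. The only figure taken from the plan is 15 patients per arm (Sample size and justification).

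**Step 1: what the rule counts.** Focus groups belong to Part I, so for a Part II patient the rule reduces to: compliant if the booklet is returned. Suppose, hypothetically, that all 30 booklets return, 3 of 15 controls obtain an MRI and 1 of 15 MRI-arm patients is never scanned. The rule reports 30/30 = 100%. Actual receipt of allocation is (12 + 14)/30 = 26/30 = 86.7%.

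**Step 2: whether another section fills the gap.**
- Quantitative process data: centre description, participation, attrition and drop-out. There is no count of scans.
- Data Analyses, Methods: recruitment process documentation. This concerns entry to the trial, not treatment received.
- Interviews: 4-6 patients and 2-4 practitioners, on acceptability and implementation. These cannot give a rate by arm.
- Quality Assurance, Study Conduct: an audit that includes adherence to protocol procedures, at least annually, in a study of about 28 to 40 weeks. It is document quality assurance, not a trial outcome.

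None yields receipt of allocation by arm.

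**Step 3: how likely the rule is to misclassify someone.** The chance of at least one non-adherent patient in an arm of 15 is 1 - (1 - p)^15. The rates p are assumptions:
- p = 5%: 54%
- p = 10%: 79%
- p = 20%: 96%

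Every such patient who returns the booklet is labelled compliant.

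**Step 4: effect on a definitive trial.** Let c be the share of controls who obtain an MRI and m the share of the MRI arm not scanned. If the effect acts only through having the MRI and is the same on average in all patients, the intention-to-treat contrast is multiplied by (1 - c - m) and the required N by 1/(1 - c - m)^2. With assumed rates:
- c = 10%, m = 5%: 1/0.85^2 = 1.38
- c = 20%, m = 10%: 1/0.70^2 = 2.04

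**Step 5: how well this trial could estimate the rates.** Exact (Clopper-Pearson) 95% intervals with n = 15:
- 0/15: 0% to 21.8%
- 1/15: 0.2% to 31.9%
- 3/15: 4.3% to 48.1%

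For 3/15 in one arm and none in the other, the inflation factor at the estimate is 1/0.80^2 = 1.56. At the interval limits it runs from 1/(1 - 0.043)^2, about 1.1, to 1/(1 - 0.481)^2, about 3.7.

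**Step 6: whether adherence can be defined on the present text.** The RCT inclusion criteria ask for an MRI and report in the last month. Study Configuration and Recruitment randomise patients to have or not have an MRI. Study Management describes one group scanned in the last month and one not scanned. The Synopsis eligibility for Part II mentions no MRI. If control patients enter already scanned, a rule of no MRI after randomisation would again show full compliance with no contrast between arms.

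**The case against.** The strongest reply is that the compliance sentence drives nothing: no analysis set, progression criterion, stopping rule or sample size refers to it, and the study has 30 patients. Interviews, end-of-site staff meetings and the audit all touch on trial procedures. The content of the CRF is not shown, and how adherence is summarised could be left to an SAP.

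Part of this stands. Adherence is not wholly ignored; what is missing is a quantitative measure by arm. The reply does not remove the point, because the protocol does not leave compliance open. It defines it, and the quantitative process data it then lists do not supply the missing count.

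Four stronger readings are tempting, but the document does not support them:
- A reader might infer that adherence to allocation is the trial's main question. The primary objective names acceptance and healthcare reliance. Adherence is behavioural evidence for that objective but is not itself named, and recruitment rate and reasons for non-recruitment do not depend on it.
- A reader might infer that the plan assumes no dilution. It gives no method, effect, SD or power for the definitive trial. It is silent on inflation and does not set the factor to 1.
- A reader might infer that control crossover is the likeliest way the design fails. The background makes it foreseeable but gives no rate, and the conflict between eligibility and arms is the more certain problem.
- A reader might infer that the observed rates could fix the definitive sample size. Step 5 shows they are too imprecise for that.

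**Conclusion.** The point holds as a defect in a stated definition. Booklet return is presented as compliance for RCT patients, it cannot distinguish patients who received their allocation from those who did not, and no other section specifies a count by arm. It bears on the protocol-integrity objective, on the evidence for feasibility of randomising, and on sizing the definitive RCT.

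The textual conclusion needs no assumption. The size does: the factors 1.38 and 2.04 rest on assumed non-adherence and on the dilution model in step 4, and they illustrate scale rather than an effect of this protocol. Correction is worthwhile before enrolment, since scans obtained elsewhere may be hard to reconstruct afterwards.

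**What to change.** 1. Relabel booklet return as data completeness.
2. Reconcile the RCT inclusion text (MRI in the last month) with the no-MRI control arm in Study Configuration, Study Management and Recruitment. Adherence cannot be defined until these agree.
3. Then record by arm, from the hospital record plus one final-booklet question on scans obtained elsewhere: in the MRI arm, MRI done and result discussed before the first physiotherapy session; in the control arm, any lumbar MRI up to the final booklet; in both arms, physiotherapy sessions attended.
4. Report the proportions by arm with exact 95% intervals and state that they are wide.
5. Use them to inform the definitive sample size over a range of dilution, not as a single inflation factor.

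The cost is three or four CRF fields and one booklet question, with no extra staff or procedures. Care is unchanged; only what is recorded changes.
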